Statistical analysis. Group descriptive statistics will be performed on all variables. Normality of distribution will be assessed by the Lilliefors test, and homogeneity of variance will be examined with the Levene test. Inter-group differences will be analyzed by one or two-way ANOVA using the Holm-Sidak test for comparison. For animal research, based on our previous studies over many years, 6-8 mice per group will be needed (and all studies performed in duplicate) on average in each group to achieve a probability of 88% that the study will detect a relationship between independent and dependent variables at a two-sided 5% significance level. This power calculation assumes that the true change in the dependent variables is 0.53 standard deviations per one standard deviation change in the independent variable. For human subjects work, based on the humanized mouse data in **Figure 4** and our publication [30], a sample size of 20 human donors per group achieves 96% power to detect a small effect size ($f^2 = 0.08$) attributed by patient category by an F-test with an $\alpha = 0.05$, when adjusting for 7 additional explanatory variables.

Overall Strategic Plan. De-identified stool samples collected at RUMC will be sent to Caltech for colonization of mice, as we have been doing for over 2 years. Additional samples for ongoing enrollment will be collected at RUMC and UW. Fecal swabs from all samples will be sent to UCSD for microbiome profiling (metagenomics). All samples will be coded so that investigators at Rush and UW can link it back to the subjects. Investigators from UCSD, Caltech and Purdue will not have access to the link to the codes with subject identifiers. Fibers will be developed and optimized in bioreactors at Purdue. Fecal samples and dietary fibers will be sent to Caltech, where all mouse treatments will take place. Fecal samples from Rush will also be sent to the [name] lab at Purdue to perform *in vitro* fermentation tests. The [name] laboratory will administer the motor tests, assess neuroinflammation, and measure α Syn aggregation; while the [name] laboratory will perform the CLARITY analysis and neuronal activity tests. Finally, fecal samples from mice will be sent to UCSD for metagenomics, and to Purdue for *in vitro* fermentation and SCFA analysis. We predict that specific, molecular interactions

Formatted: Font: Italic

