Gut bacteria influence the differentiation and function of immune cells in the intestine, periphery and brain [34-36]. Intriguingly, subjects with PD exhibit intestinal inflammation [37], and GI abnormalities such as constipation often precede motor symptoms by many years [38, 39]. Braak's hypothesis posits that aberrant α Syn accumulation initiates in the gut and propagates via the vagus nerve to the brain [40]. This notion is supported by pathophysiologic evidence: α Syn inclusions appear early in the ENS, and the glossopharyngeal and vagal nerves [38, 41], while vagotomized people are at reduced risk for PD [42]. Further, injection of α Syn fibrils into gut tissue of healthy rodents induces pathology within the vagus nerve and brainstem [43]. However, the notion that α Syn aggregation initiates in the ENS and spreads to the CNS via retrograde transmission remains controversial [44], and experimental support for a gut microbial connection to PD is lacking.

Gut bacteria and diet. Microbiota composition and function are shaped over the course of an individual's life and depend on many factors including a significant role for diet [4]. In humans and mice, both long-term dietary patterns [45] and rapid, extreme dietary changes [46] can shape and re-shape the representation of microbial taxa and their functional attributes. Since many of the precursor molecules available for microbial metabolism are provided by diet, altering diet can alter the metabolic output of the microbiome. Broad effects of diet on the microbiome and its associated metabolome were observed when humanized mice were switched from standard mouse diets to a high sugar, polysaccharide-deficient diet [47]. Although mice harboring microbiotas from three different humans showed distinct composition, metabolomic fingerprints of the three groups were remarkably similar when fed the same diet [47], illustrating conservation of microbial metabolism. The principle of dietary impacts to the metabolic output of the microbiome has also been established in humans [48].

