Experimental Approach. We have already collected and biobanked fecal and blood samples from 40 well-characterized (including 20 newly diagnosed, treatment naïve) PD patients and 20 matched [for age, gender, race, BMI] healthy controls (HC). We also have comprehensive dietary information (using 24 hour diet recall questionnaire prior to stool collection) in these subjects. To profile the human fecal microbiome, DNA will be extracted using the NexteraXT sample preparation kit adapted for acoustic liquid handling, and subjected to whole-genome shotgun metagenomic sequencing. This procedure is routine to our team [87-90], but briefly, shotgun metagenomics will be performed using the NexteraXT barcoded kit on the Labcyte Echo and TPP Mosquito platforms, allowing low-biomass inputs. Sequencing will be performed at 2X150 bp using the Illumina HiSeq 4000 platform, allowing excellent depth of coverage, and mapped to ~47,000 reference bacterial genome sequences using HUMAnN2. In our experience, assembly using metaSPADES [91] does not work well for data generated using this method, but when the reference genome collection is fairly complete, as it is for human stool microbiomes, read mapping provides excellent taxonomic and functional results. Bioinformatics analyses using HUMAnN2 and QIIME [92] will map metagenomic DNA data sets to determine gene content and the corresponding microbial pathways involved. Though we will mine this data exhaustively for global multi-parameter analysis, we will specifically determine whether genes associated with known SCFA pathways are enriched or depleted differentially in PD patients and controls.

Our hypothesis is that microbiota-derived metabolites contribute to PD symptoms, and may be protective or pathogenic depending on metabolite levels and/or ratios. The question is whether hallmark changes in microbiome composition and function are specific to PD or are the consequence of aggregated α Syn in the ENS and intestinal dysfunction. To answer this question, we will collect stool samples from patients with Multiple System Atrophy (MSA), a synucleinopathy, and α -synuclein-dementia [n=20 each group], and interrogate their microbiome composition and function using shotgun metagenomics as described. Comparison to the PD microbiome will address specificity to related neurodegenerative disease, and this knowledge could also further expand the role of microbiome to additional disorders where α Syn plays a pathogenic role.

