Aim 1.2. Identify the potential contributing factors for dysbiosis in PD

Rationale. It is well established that environmental factors such as diet, as well as genetics, impact microbiome composition [93]. Currently, there are no data for how environment impacts the microbiome in PD. Filling this knowledge gap can advance our understanding of the underlying mechanism of dysbiosis in PD and provide an opportunity for disease modification in those at high risk of developing PD, such as first-degree relatives.

Experimental Approach. In order to determine the contribution of environmental and genetic factors to dysbiosis in PD, we propose two approaches. First, a cross sectional study where we will compare microbiome composition in subsets of PD patients (newly recruited as part of the proposed application) whose household, non-related spouse (for environmental factor) and their first-degree relatives who do not live with the patient agree to provide stool samples as well. The consent process will be initiated after the subject has been initially screened for eligibility. If the patient meets inclusion and exclusion criteria, the subject will be approached by a member of the study staff during his/her regular clinic visit or sent a copy of the consent form so that they may read it in the comfort of their own home. If the potential subjects' spouse/ relative accompany during the clinic visit, they will be informed about the study. If not, the subject will be asked to share the study information with their spouse/ relative and inform the study team if interested. If the subject is interested in moving forward, the consent will be reviewed by the study coordinator in the Gastroenterology clinic. The study coordinator, PI or study staff delegated the responsibility by the PI will obtain informed consent from the subject.

We also plan to have the study registered on clinicaltrials.gov and the Michael J Fox trial finder so that interested participants can contact the study team.

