Each household and first-degree relative study subject will be evaluated to ensure there is no clinical evidence of neurological disorders including PD. Also, these subjects will complete a 24 hour diet recall questionnaire before stool collection and validated 3 month food frequency questionnaires to collect dietary information similar to PD patients. Each subject (including PD subjects) will complete a smell questionnaire and a sleep questionnaire to determine whether these “control” subjects have loss of smell or have REM sleep disorders because these

conditions increase the risk of PD. For assessing smell, we will use the UPSIT questionnaire [94, 95]. For assessing REM sleep disorder, we will use RBD1Q which consists of a single question, answered “yes” or “no,” as follows: “Have you ever been told, or suspected yourself, that you seem to ‘act out your dreams’ while asleep (for example, punching, flailing your arms in the air, making running movements, etc.)?” [96] We predict that at least 20 PD patients/MSA will have both household spouse and first degree relative willing to provide stool samples for this study.

Second, in the longitudinal study, we will collect stool every 3 months (with 3 day diet questionnaire prior to each collection) over 12 months and determine microbiome composition over time. All PD subjects will undergo clinical assessments at baseline and end of the study to determine the severity of PD. These assessments will include: Movement Disorder Society-Sponsored Revision of the Unified Parkinson’s Disease Rating Scale (MDS-UPDRS); Hoehn and Yahr Stage (HY); Non-Motor symptoms Scale (NMSS); Montreal Cognitive Assessment (MoCA). We will correlate the microbiome data with PD symptoms, diet and response to treatment and progression of disease. These studies will determine whether disease progression and factors such as PD medications and diet significantly impact microbiome composition. Further, we will determine whether changes in SCFA-producing bacteria (as part of Aim 1.1) and/or abnormal SCFA profiles (as part of Aim 1.3) correlate with severity of PD symptoms.

Inclusion/ Exclusion Criteria:

For Parkinson’s disease subjects:

Inclusion criteria:

1. 40-80 years of age
2. Documented diagnosis of Parkinson’s disease
 - For cross sectional study- the Parkinson’s disease stages 1-4 are eligible
 - For longitudinal study- the Parkinson’s disease stages 1-2.5 are eligible

Exclusion criteria:

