1. History of GI diseases (except for hemorrhoids or occasional (<3 times a week) heartburn) like Inflammatory bowel disease or Celiac disease
2. Antibiotic use within last 12 weeks
3. Use of probiotic supplement except yogurt
4. Intentional change in diet
5. Chronic use of NSAIDS. A washout period of 3 weeks is needed before the subject could be enrolled into the study. Low dose aspirin is allowed

For household controls/ 1st degree relatives:

Inclusion criteria:

1. 40-80 years of age
2. No clinical evidence of neurological disorders including Parkinson’s disease
3. Live in the same household as the Parkinson Disease patient or is a first degree relative of the PD patient

Exclusion criteria:

1. History of GI diseases (except for hemorrhoids or occasional (<3 times a week) heartburn))like Inflammatory bowel disease or Celiac disease
2. Antibiotic use within last 12 weeks
3. Use of probiotic supplement except yogurt
4. Intentional change in diet
5. Chronic use of NSAIDS. A washout period of 3 weeks is needed before the subject could be enrolled into the study. Low dose aspirin is allowed

Aim 1.3. Determine how dysbiosis promotes PD pathogenesis by correlating microbiomes to metabolites

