
Expected Outcomes for Specific Aim 1. We anticipate confirming our prior findings that patients with PD have dysbiosis, and further identifying the nature of the dysbiosis including changes at the species and strain level. We will extend these studies via metagenomic analysis to quantify butyrate-producing bacteria and gene pathways involved in SCFA production, which we predict will be different between PD patients and HCs. We anticipate defining correlations between PD status, dysbiosis and SCFAs. We anticipate that microbiome composition in first-degree relatives is more similar to PD subjects than to HCs. We predict that patients with other forms of α -synucleinopathy have dysbiosis, but that their microbiomes are different from PD patients. Indeed, our pilot data using 16S rRNA analysis in 6 patients with MSA show distinct dysbiosis from PD (data not shown). We predict that patients with PD have abnormal SCFA ratios in stool and serum, and will carefully determine levels of all detectable SCFAs in order to determine disease-related profiles. We cannot predict microbiome stability in PD patients, but anticipate that there will be variation in the microbiome over time, but that dysbiosis will remain throughout the year with persistence in abnormal SCFA profiles.

[figure not shown]

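### Aim 1.2: likeness between patients and relatives who live apart mixes genes with an earlier shared home, so it cannot be read as a genetic contribution

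*Protocol*

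**What the plan says.** The purpose is given at the start of the Experimental Approach of Aim 1.2: "In order to determine the contribution of environmental and genetic factors to dysbiosis in PD, we propose two approaches". The first approach is cross-sectional. It takes newly recruited patients whose household "non-related spouse (for environmental factor) and their first-degree relatives who do not live with the patient agree to provide stool samples". Only the spouse carries a label.

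The inclusion criteria for household controls and relatives ask for "40-80 years of age", no clinical evidence of neurological disorder, and this: "Live in the same household as the Parkinson Disease patient or is a first degree relative of the PD patient".

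From these participants the protocol collects a 24-hour diet recall, a 3-month food frequency questionnaire, and smell and sleep questionnaires. It expects that "at least 20 PD patients/MSA will have both household spouse and first degree relative willing to provide stool samples".

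The background section on gut bacteria and diet states: "Microbiota composition and function are shaped over the course of an individual's life and depend on many factors". The expected outcomes for Aim 1 add: "We anticipate that microbiome composition in first-degree relatives is more similar to PD subjects than to HCs".

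**The concern.** The design pairs each patient with someone who shares the home but not the genes, and with someone who shares genes but not the current home. If those were the only differences, comparing the two kinds of pair would say something about environment and genes. They are not the only differences. A sibling normally grew up with the patient, and a child or parent normally lived with the patient for years. Requiring relatives to live apart removes present cohabitation and leaves past cohabitation in place.

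What is at stake is the conclusion of this sub-aim. Its rationale speaks of disease modification in people at high risk, naming first-degree relatives. If familial likeness is reported as genetic, attention may turn away from early exposures that could be modified.

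**Working it through.** The plan gives no figure for this comparison, so there is none to reproduce. The check sets the stated purpose against what the groups can identify.

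**1. What each contrast contains.** Let E be the effect of the current shared home, G of shared genes, H of an earlier shared home, and A of the age difference within the pair, each as a contribution to likeness with the patient.

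- Patient with unrelated household spouse: E.
- Patient with relative living apart: G + H + A.

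That is two contrasts for four unknowns. If age is handled by adjustment, two contrasts remain for three unknowns (E, G, H). E can be read from the spouse pairs under this simple model, but G and H appear only as a sum.

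**2. Why the sum cannot be split.** With values chosen only for illustration and A = 0:

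- G = 0.3, H = 0 gives 0.3
- G = 0.2, H = 0.1 gives 0.3
- G = 0, H = 0.3 gives 0.3

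All three produce the same observed likeness. A larger sample would estimate 0.3 more precisely but would not tell the three cases apart.

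**3. Whether planned data could split it.** The items listed for spouses and relatives concern current or recent diet, smell and sleep. Neither co-residence history nor host genotyping is described. The second approach of Aim 1.2 follows microbiome composition over 12 months and relates it to symptoms, medication and diet; it does not address genes.

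**4. Whether eligibility enforces the intended groups.** Cross residence with kinship:

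- Lives with the patient, unrelated: admitted, and intended if a spouse.
- Lives apart, first-degree relative: admitted and intended.
- Lives with the patient, first-degree relative: admitted by the criterion, but in neither group that Aim 1.2 describes.
- Lives apart, unrelated: not admitted.

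The criterion admits three of the four cells and the aim describes two. It requires neither that relatives live apart nor that household members be unrelated.

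**5. Age, as a secondary point.** With a lower limit of 40, a patient of 70 may bring a child up to 70 − 40 = 30 years younger, and a patient of 65 one up to 65 − 40 = 25 years younger. A sibling would usually be much closer in age. No alignment of age within families is stated.

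**The case against.** Several points on the other side have force.

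- **The genetic reading is inferred.** The protocol never calls relatives the genetic comparison and defines no partition, and the sub-aim speaks of potential contributing factors. Its prediction about relatives and healthy controls does not name genes. This stands as a limit on wording. But the stated purpose names two factors and assigns the spouse to one of them, and the living-apart condition has little use except to isolate the other.
- **Early home may fade.** The same background section says that rapid, extreme dietary changes can also reshape the microbiota, and current diet is measured. This is fair: the protocol does not show that an early home persists. It does not show the opposite either, and the plan has no means of finding out.
- **Age and sex can be left to the analysis.** The Statistical analysis section foresees 7 further explanatory variables without naming them, and age and sex may be among them. This stands, so age is only a secondary point. It does not help with co-residence, because no later model can adjust for what was not recorded.
- **Every family design without twins or adoptees has this limit.** True. It argues for a modest label rather than for silence.

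A reader might also infer that the age gap biases the comparison by a known amount. The documents give no correlation between relatives and no change of the microbiome with age, so any such figure would be invented. Nor do they support an age mismatch in the comparison of relatives with healthy controls: those controls are matched on age, so a relative's age gap enters the distance to patients and the distance to controls alike and largely cancels, provided the newly recruited patients resemble the biobanked ones in age.

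**Conclusion.** The concern holds in a limited form. The plan can describe likeness between patients and relatives who live apart, but it cannot attribute that likeness to genes. The conclusion rests on two things that the documents do not state outright: that the relatives serve as the genetic comparison, which the purpose implies, and that most of them once lived with the patient, which is a reasonable assumption that the protocol neither records nor excludes.

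The size cannot be given. The share due to an earlier home could lie anywhere from none to all of the observed likeness. The effect is confined to the interpretation of one exploratory sub-aim; the comparison of patients with healthy controls in Aim 1.1 is untouched. It is worth acting on because co-residence history is easiest to collect at enrolment. The mismatch between the eligibility criterion and the groups in Aim 1.2 is a plain inconsistency and should be reconciled in any case.

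**What to change.** 1. At enrolment, record the type of relative (parent, sibling, child), the years lived with the patient and the years since.
2. Report likeness in relatives as familial (genes or earlier shared home), not as genetic.
3. Use co-residence history descriptively or in a sensitivity analysis among relatives only. Years since living together is zero for every household spouse and positive for nearly every relative living apart, so in a joint model it almost duplicates the type of pair. About 20 families cannot support more.
4. Align the inclusion criterion with Aim 1.2 by stating whether relatives must live apart and whether household members must be unrelated spouses.
5. Name age among the covariates already planned.

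Two tempting additions should be avoided. Preferring siblings narrows the age gap but selects relatives who shared a childhood home. Calling likeness genetic when it does not decline with years apart is unsound: about 20 families could easily miss a decline, and a lasting early-life effect would show none.

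The cost is two or three form items, one sentence of eligibility text and a more modest claim. No extra subjects are needed.

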in each motor task described in Figure 3. $**p \leq 0.01$; $***p \leq 0.001$; $****p \leq 0.0001$. HC=germ-free mice colonized with fecal microbes from healthy controls, PD=germ-free mice colonized with fecal microbes from Parkinson’s disease patients, WT=wild-type, ASO=Thy1- α -synuclein genotype. Note: for all 6 individual pairs, mice with PD microbiota performed worse in most or all tests compared to HCs. Also, we have not excluded any fecal samples tested in this data set, thus these results appear to be robust.

Specific aim 1. Profile the human stool microbiome, and serum and stool SCFA levels, in early PD patients and matched healthy controls

Introduction. We [30] and others [31] have shown that patients with PD have abnormal microbiota compositions. These data support the hypothesis that the human microbiome could either trigger PD or impacts PD disease course. However, several questions remain to be answered: (1) what is the exact nature of the dysbiosis in PD and how specific is the dysbiosis for PD compared to other synucleinopathies? (2) what are the contributing factors for the observed dysbiosis? and (3) how does the dysbiosis promote PD pathogenesis? The objective of this aim is to fill the translational knowledge gap between dysbiosis of the microbiome and PD.

Aim 1.1. Comprehensively interrogate microbiome composition to elucidate the exact nature of the dysbiosis in PD and to determine whether the observed dysbiosis is specific for PD

Rationale. The currently published data on microbiome composition present in PD utilized targeted approaches

such as 16S rRNA pyrosequencing [30, 31]. These techniques provided accurate assessment of microbiota composition to the genus level, but are not adequate to provide species or strain level determination and thus

further studies using next generation sequencing and advanced bioinformatics are needed to comprehensively interrogate microbiome composition. This approach provides very detailed information about the microbiome that may enable better understanding of host-microbial interaction processes, and may identify bacteria that are either missing or over-representing in the PD subjects, possibly providing leads toward identification of bioactive species for study in Aim 4 and future research.

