Introduction. Our preliminary data in **Figure 4** reveal that microbiota transplant from early onset PD patients exacerbates disease in ASO mice compared to gut bacteria from healthy controls. However, we did not measure SCFA levels in donors at time of collection, as sampling was prior to our current knowledge. Here, we will transplant microbiota into WT and ASO mice from high (top 3rd) and low (bottom 3rd) SCFA producers, aiming for 6 PD and 6 HC donors for each (24 total groups). We will assess motor symptoms and gut motility. Neuroinflammatory status will be determined, and α Syn aggregation measured in the gut and brain. We will extend our current data to measure neurodegeneration in the enteric nervous system and various brain regions using tissue clearing by CLARITY. CLARITY will be used to measure neuronal activation through cFos staining in fixed postmortem tissue; to corroborate and expand these results, we will perform real-time calcium imaging and electrophysiology in living tissue from humanized mice. These studies will reveal functional links between the microbiome and PD pathophysiology, and test SCFAs as a mediator of gut-brain connections.

Rationale. Novel AAV tools to study cellular populations. Genetically-encoded tools that can be used to visualize, monitor, and modulate mammalian neurons are revolutionizing neuroscience. The [name] lab has recently published an *in vivo* selection platform (CREATE) for identifying adeno-associated viruses (AAVs) that more efficiently transduce genetically defined cell populations. The CREATE platform has already demonstrated one novel vector with intravascular delivery, AAV-PHP.B, that is 40- to 90-fold more efficient at transducing the brain than the current standard, AAV9 [101]. AAV-PHP.B transduces most neuronal types and glia across the brain. We also possess a novel, unpublished capsid (PHP.S) identified in the screen that has increased affinity for peripheral neurons over PHP.B or the widely used AAV9 (**Figure 5**).

systemically-delivered AAV-PHP.S appears brighter and labels fine processes (arrow) compared to (B) AAV9 in PACT-cleared duodenal cross sections of the mouse gut. (C) Individual neurons in enteric ganglia are distinctly colored, enabling tracing of individual neuronal processes. (D) Locally delivered synapsin-driven channelrhodopsin via AAV-PHP.S spatially restricts expression in enteric ganglia and limits photostimulation area. (E1) Systemic delivery of AAV-PHP.S

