Experimental Approach. Behavioral analysis of colonized mice. Prior to colonization, mice will be systemically injected with AAVs that contain promoter constructs to label Tyrosine Hydroxylase (TH) for dopaminergic neurons or Synapsin for all neurons. Wild-type (WT) or Thy1-ASO (ASO) mice raised in germ-free conditions will receive fecal transplants of high and low SCFA producing microbiota derived from PD and HC donors. After allowing 6 weeks of colonization, mice will be assessed for motor deficits and gut motility. After motor testing, mice will be sacrificed and tissues analyzed using CLARITY, as described below.

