
After testing, mice will be sacrificed and prepared for either histology or physiological recordings. For these particular studies, we will colonize 12 mice per condition and all will undergo behavioral evaluation. Within each condition and as described below, tissue from 4 mice will be evaluated for histology, 4 for population activity imaging, and 4 for whole cell patch clamp electrophysiology.

Histological evaluation of neuronal populations in cleared brain and GI tissue. Mice will be sacrificed via intracardial perfusion with 4% paraformaldehyde. To enable fine-scale neural circuit mapping in a whole unsectioned specimen by light microscopy, the opaque sample needs to be "cleared" to allow light penetration

throughout the whole sample. One effective tissue clearing technology, CLARITY, creates tissue-hydrogel hybrids that lock in place bio-macromolecules and are amenable to selective lipid extractions to increase optical

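### Aim 2's diagnosis and SCFA contrasts vary only between donors, but the planned ANOVA counts mice and has no donor term, so both will be declared significant too often

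*Protocol*

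**What the plan says.** The introduction to Specific aim 2 plans to "transplant microbiota into WT and ASO mice from high (top 3rd) and low (bottom 3rd) SCFA producers". The number of donors intended in each SCFA class follows in the same sentence: "aiming for 6 PD and 6 HC donors for each (24 total groups". The Experimental Approach of that aim confirms that mice are the recipients: WT or ASO animals "will receive fecal transplants of high and low SCFA producing microbiota derived from PD and HC donors". On numbers it says "we will colonize 12 mice per condition and all will undergo behavioral evaluation", without defining a condition.

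The analysis rule is in the Statistical analysis section: "Inter-group differences will be analyzed by one or two-way ANOVA using the Holm-Sidak test for comparison". The animal sample size there is "6-8 mice per group will be needed (and all studies performed in duplicate) on average in each group". The stated purpose of that number is "to achieve a probability of 88% that the study will detect a relationship between independent and dependent variables". That section names no donor factor, nesting, random effect or averaging to donor. Its one calculation in donors (20 per group) is labelled human subjects work.

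**The concern.** A mouse's PD/healthy label and its high/low SCFA label are both fixed by whose stool it received. The conclusion sought is about PD versus healthy, and high- versus low-SCFA, microbiota in general, so it must hold over donors. Donor-to-donor variation enters these two contrasts in full. A mouse-level error term treats mice with the same donor as independent and understates that variation.

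The Protocol itself expects such variation. Aim 4.1 reports that recipient mice resembled their own donor's microbiome most closely, and it picks the three pilot PD donors with the most severe symptoms out of six. Chance differences between a few donors could then be read as an effect of disease or of SCFA production.

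The point covers only these two contrasts. Genotype in Aim 2 and treatment in Aims 3.2, 4.1 and 4.2 vary within donor and do not share the fault.

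**Working it through.** **1. The Protocol's own figure.** Inputs: standardised slope r = 0.53, two-sided 5%, 6-8 mice per group, in duplicate. With f² = r²/(1 − r²) = 0.2809/0.7191 = 0.391, noncentral-F power for a slope is 88.9% at 28 mice (2 groups × 7 mice × 2 replicates), 83.3% at 24 and 92.8% at 32. With 14 mice it is only about 58%. The stated 88% is therefore reached when every mouse, duplicates included, counts as independent. This is one reading, but it fits a mouse-based n.

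**2. Numbers of donors and mice.** Two diagnoses × two SCFA classes × 6 donors = 24 donors, 12 on each side of each main effect. The undefined condition allows two readings:

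- one donor's mice of one genotype: 24 × 2 × 12 = 576 mice, 12 per donor and genotype;
- one diagnosis × SCFA × genotype cell: 4 × 2 × 12 = 96 mice, 12/6 = 2 per donor and genotype.

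The valid error term for diagnosis or SCFA has 24 − 4 = 20 df. A two-way ANOVA on mice would use 96 − 4 = 92 to 576 − 4 = 572.

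**3. Type I error.** The Protocol gives no ICC, so 0.05-0.30 is assumed. Null data were simulated (40,000 sets per setting) with donor variance = ICC and within-donor variance = 1 − ICC, then analysed by two-way ANOVA (diagnosis × SCFA) on mice. Rejection rates for diagnosis at nominal 5% were as follows; those for SCFA agree within 0.01.

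| Mice per donor in the analysis | ICC 0.05 | 0.10 | 0.20 | 0.30 |
|---|---|---|---|---|
| 2, one genotype | 0.057 | 0.060 | 0.076 | 0.085 |
| 6, one genotype | 0.079 | 0.114 | 0.172 | 0.223 |
| 8, one genotype | 0.092 | 0.134 | 0.210 | 0.274 |
| 12, one genotype | 0.118 | 0.180 | 0.281 | 0.357 |
| 2 per genotype, both pooled (96 mice) | 0.068 | 0.087 | 0.123 | 0.162 |
| 12 per genotype, both pooled (576 mice) | 0.180 | 0.283 | 0.415 | 0.497 |
| Donor as unit, any row | 0.048-0.052 | | | |

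At ICC 0 the mouse-level test is also at 5%. The pooled rows assume the same donor effect in both genotypes and no genotype difference. A large genotype effect left out of the model would enlarge the mouse error and lower them.

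**4. Check by formula.** The design effect is 1 + (m − 1) × ICC. For m = 12 and ICC 0.20 it is 1 + 11 × 0.20 = 3.2. Then 1.96/√3.2 = 1.096, a two-sided tail of 0.273 against 0.281 simulated. For m = 2 it is 1.2, giving 0.074 against 0.076.

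**5. Other readings.** If the 24 groups mean 12 donors × 2 genotypes, 12 mice per donor in one genotype gives 0.118-0.366. If each donor is a group in a one-way ANOVA, a PD-versus-healthy contrast against mouse error rejects at 0.16-0.46 for ICC 0.20 and 96-576 mice.

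**The case against.** The strongest reply is that the Statistical analysis section is one generic paragraph for four aims. It does not say that Aim 2 mice are pooled over donors, and an ANOVA on donor means is itself a two-way ANOVA. The error term could be left to a SAP. The same section also sizes donors, 20 per group, for a patient-category effect. This does not clear the plan. The paragraph names both the test and the unit of n for animal work, and that unit is the mouse. The donor calculation is labelled human work and matches neither 6 per cell nor 12 per diagnosis. A SAP would have to override this text, not fill a gap in it.

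Three points stand in part:

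- **Size is conditional.** The ICC is assumed and mice per donor are unknown. With 2 per donor and one genotype, inflation is small. On that reading the tissue assays, with 4 mice each per condition, have fewer than one mouse per donor (4/6), so little inflation remains there.
- **Holm-Sidak lowers the rates but does not cure them.** With a Sidak threshold over the two main effects, 1 − √0.95 = 2.5%, each effect rejects at 7.1-29.6% with 12 mice per donor and 2.9-5.3% with 2.
- **The consequence is limited.** Aim 2 is preclinical, and donors for later aims are chosen from Aim 1 or the pilot, not on Aim 2 significance. What is at risk is Aim 2's own conclusion.

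**Conclusion.** The concern holds. The stated rule gives the wrong error term for the diagnosis and SCFA contrasts in Aim 2, and the direction is the same under every reading of groups and conditions. Within one genotype and for an assumed ICC of 0.05-0.30, the true error rate of a nominal 5% test is about 12-36% with 12 mice per donor, 8-27% with 6 to 8, and 6-9% with 2. Pooling genotypes raises it to 7-16% (96 mice) or 18-50% (576 mice) under the assumptions above. The inflation vanishes only if donors of the same diagnosis and SCFA class do not differ at all, which the Protocol's own pilot remarks make unlikely. This should be fixed before Aim 2 is analysed.

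**What to change.** In the Statistical analysis section, state that the donor is the experimental unit for the Aim 2 diagnosis and SCFA contrasts. Then do one of two things:

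- run the two-way ANOVA (diagnosis × SCFA) on donor means within each genotype; or
- fit a mixed model with genotype, diagnosis and SCFA class as fixed effects and a random donor intercept. This also holds all three factors, which a two-way ANOVA cannot.

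Report donors (6 per cell, 12 per diagnosis) as the effective sample size. In the Aim 2 Experimental Approach, define a condition and give mice per donor and genotype. The pilot was already summarised by donor: "for all 6 individual pairs, mice with PD microbiota performed worse in most or all tests compared to HCs". A donor-level analysis is therefore feasible.

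The cost is wording and wider intervals, with no extra mice or donors. As an illustration, take the Protocol's generic effect, d = 2r/√(1 − r²) = 1.06/0.848 = 1.25, and the variance of a donor mean, ICC + (1 − ICC)/m. Over ICC 0.30 down to 0.05, power within one SCFA class (6 donors per arm, 10 df) is 90% to above 99% with 12 mice per donor, 86-99% with 6, and 68-77% with 2. Pooled over SCFA classes (12 per arm, 20 df) it is at least 95% in all these cases. The 0.53 slope was not stated for PD versus healthy microbiota, so these figures do not promise that power.
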